Targeted skill-building to address care recipient symptoms (and other stressors) elicited from participants is integrated into the session to maximize training in skills pertinent to the group. Discussion is focused around challenging symptoms of dementia experienced by participants and skills to address these symptoms are interwoven into the discussion. Prepared handouts are given to participants that focus on specific symptoms and behaviors elicited during group discussion (See Appendix 3 for examples).

Self-care activities from the previous session are briefly discussed and continued self-care is emphasized. Sleep hygiene education and discussion is included due to the fluctuations in sleep [53] most likely due to the demands of care provision and sleep problems [54, 55] in caregivers. Exercise commensurate with physician approval is also promoted due its effects on sleep [56] in addition to its general paucity in caregivers [57].

The relaxation technique covered in Session 2 is deep breathing (See Appendix 4), including instruction and practice sessions. Continued home use (instructional materials provided) is encouraged with participants setting self-made goals for implementation.

2.A.3.e.2c. ESBR Session 3 – Dementia: How can I best communicate with my sources of support?

Session 3 objectives are to:

- build caregiver communication skills (~50 minutes)
- emphasize the importance of self-care (planned pleasant activities) (~20 minutes)
- introduce the relaxation technique of progressive muscle relaxation (~20 minutes)

Session 3 is designed to enhance the caregiver’s ability to communicate with family, friends, and health care providers (both those of their care recipient and their own). Targeted skill-building geared toward effective communication is the focus of this session. Role play is utilized to give participants practice using effective communication techniques for interactions with family and friends. Skill-building targeted at improving caregiver/health care provider communication is modeled after the National Institute on Aging publication *Talking with your doctor: a guide for older people* (participants are provided with a copy of the publication to supplement the session). Communication tools,

preparing for a healthcare appointment, getting information from healthcare providers, and partnering with healthcare providers to make decisions are addressed in detail. Assistance and direction with planning for future care needs is reviewed and social work referrals are encouraged. See Appendix 2 for content samples.

Self-care activities from the previous sessions are briefly discussed and continued self-care is emphasized. This session will specifically focus on planning pleasurable activities.

The relaxation technique covered in Session 3 is progressive muscle relaxation (See Appendix 4), including instruction and practice sessions. Continued home use (instructional materials provided; audio segments are provided for use at home via the modality of caregiver preference) is encouraged with participants setting self-made goals for implementation.

2.A.3.e.2d. ESBR Session 4 – Dementia: How can I cope with the challenges and stress caused by dementia?

Session 4 objectives are to:

- build caregiver coping skills (~45 minutes)
- solidify the importance of self-care (review) (~15 minutes)
- review of learned relaxation techniques (~30 minutes)

Session 4 is designed to improve the caregiver's coping skills, specifically targeted to address the challenges of being a dementia caregiver. Ways to manage common symptoms of dementia syndromes using concrete examples, provided both by the leader of the session and caregiver participants, are demonstrated and practiced in role play. The intervention leader will aid participants in reframing cognitive, behavioral, and psychiatric symptoms of dementia as manifestations of damage to the brain. See Appendix 2 for content samples.

Targeted skill-building to address care recipient symptoms elicited from participants is integrated into the session to maximize training in skills pertinent to the group. Non-pharmacological interventions for dementia symptom management from previous sessions are reviewed and consolidated (see Appendix 3 for examples).

Self-care activities from the previous sessions (stress awareness, sleep hygiene, and planned pleasant activities) are discussed and importance of continued self-care is solidified.

The relaxation techniques covered in Sessions 1-3 are reviewed and consolidated. Continued use post-intervention is encouraged with participants setting ongoing goals for implementation.

2.A.3.e.2e. ESBR Booster Sessions (3 and 9 months post-intervention)

Booster Session objectives are to:

- review dementia and dementia resources (~20 minutes)
- polish caregiving skills (tailored to the needs of each small group) (~35 minutes)
- re-emphasize the importance of self-care (~15 minutes)
- highlight learned relaxation techniques (~20 minutes)

The booster sessions are designed to briefly review dementia knowledge and resources available to dementia patients and their caregivers (i.e., within VA, the local community, and the nation). Caregiving skills, as they pertain to current stressors, are honed in a manner that is tailored to the small group's needs. The importance of continued self-care (specifically stress awareness, sleep hygiene, and planned pleasant activities) is accentuated. Intervention relaxation techniques (i.e., guided imagery, deep breathing, and progressive muscle relaxation) are revisited and continued use is fostered.]]

2.A.3.e.3. Method of Delivering ESBR as In-clinic or Video Telehealth

For the participants randomized to our ESBR intervention (n=50 in-clinic, ESBR-i; n=50 via video telehealth, ESBR-v), all ESBR sessions will be led by [name] in groups of ≤ 10 participants. Dates and times of the group intervention will be arranged to fit participant schedules. In general, Sessions 1-4 (described above) will

be completed within 4-6 weeks. Materials (e.g., print items, audio) for each session will be provided for each participant in each intervention arm.

In-clinic ESBR Delivery: Participants in the ESBR-i (in-clinic) group will meet in person with [name] to receive the ESBR intervention. They will come to the VAPAHCS medical center division (i.e., Palo Alto, Menlo Park or Livermore) or VAPAHCS community-based outpatient clinic (CBOC) in the proximal community (e.g., San Jose, Fremont) most convenient to them.

Video Telehealth ESBR Delivery: Participants in the ESBR-v (video telehealth) group will receive [name] ESBR intervention via video telehealth technology (i.e., two-way audio and video). Clinics throughout the VAPAHCS are equipped with private rooms containing with audio/visual equipment (video camera, microphone, and display monitor) that will be used to deliver the ESBR intervention with the assistance of the local telehealth coordinator. Participants will attend the ESBR sessions at the medical center division or CBOC most convenient to them.

2.A.3.e.4. Usual Care (plus supplemental educational materials)

Participants randomized to the Usual Care (UC) group will receive supplemental educational materials (e.g., VA Caregiver Support Program, Veterans Crisis Line, National Institute on Aging publications "Caring for a Person with Alzheimer's Disease: Your Easy-to-Use Guide" and "Understanding Memory Loss").

2.A.3.e.5. Follow-up (at 6, 12, and 24 months post-intervention)

Trained study staff, blind to the participants' ESBR/UC assignment, will administer follow-up assessments at 6, 12, and 24 months after the conclusion of the intervention or assignment to usual care. These assessments will mainly occur over the telephone. Our motivation for telephone assessment is to reduce study participation burden for the participants. Packets with assessment aids will be sent to the caregiver in the mail prior to each assessment. **[[Should caregivers prefer, in-person assessments will also be offered.]]** The follow-up assessments include clinicodemographic updates and measures of caregiver cognitive status, burden, depression, self-efficacy, and health-related quality of life, in addition to care recipient functional, placement, and mortality status. (See section 2.A.3.e.6. for a detailed description of these measures).

[[2.A.3.e.6. Study Conclusion

At the conclusion of the study, all participants will be thanked for their participation. Similar to referral procedures implemented throughout the study, at the conclusion of the study all participants will be provided with referrals for services for significant stress, mental health challenges, or cognitive concerns. Mental Health referrals to Stanford Outpatient Psychiatry Clinics will be offered to all participants. Participants with cognitive concerns will be offered referrals to the Stanford/VA Alzheimer's Research Center. The Center provides a comprehensive diagnostic evaluation, including cognitive assessment, by a multidisciplinary clinical research team at no cost.]]

2.A.3.e.6. Study Measures

Study assessments will mainly occur over the telephone τ , conducted by the Study Coordinator. Our motivation for telephone assessment is to reduce study participation burden for the participants. Packets with assessment aids will be sent to the caregiver in the mail prior to each assessment. **[[Should caregivers prefer, face-to-face (in-person) τ assessments will also be offered.]]**

Primary Outcome: Caregiver Burden

Zarit Burden Interview (ZBI) [58] τ . The ZBI is a 22-item self-report measure of caregiver burden. Several version of the ZBI have been used successfully as outcome measures in interventions for dementia caregivers [22, 23, 40]. Reliability of the ZBI ranges based on time intervals between tests, but can be assumed to have moderate reliability [59-61]. The ZBI contains questions related to emotional, physical, and social strains that result from caregiving. Scores for each item range from 0 (never) to 4 (nearly always) on questions such as "Do you feel embarrassed by your relative's behavior?" Total scores are calculated by summing all responses and range from 0-88.

Secondary Outcome: Caregiver Depression

Center for Epidemiological Studies-Depression (CES-D) [62] τ . The CES-D is a 20-item, self-report measure of frequency of depressive symptoms over a one week period. The CES-D is frequently used to assess depression in dementia caregivers and has been shown to be sensitive to changes in caregiver depression post intervention [37]. It has been demonstrated to show sufficient psychometric properties [62]. Scores for each item range from 0 (rarely or none of the time) to 3 (most or all of the time), with some items reverse coded. Total scores are calculated by summing all responses and range from 0-60. A cutoff score of $>$ or $=$ 16 is used to indicate depressive symptoms considered to be comparable to prevalent depression.

[[Secondary Outcome: Community tenure τ

Based on caregiver interview and available medical records, community tenure (i.e., amount of time spent living in the community and not hospitalized or placed in a facility) and number of incidents leading to non-community status will be ascertained.]]

Secondary Outcome: Long-term Care Placement τ

Based on caregiver interview, permanent placement of the care recipient in LTC will be ascertained at all follow-up time-points. Date and level of placement will be ascertained.

Secondary Outcome: Mortality τ

Based on caregiver interview, care recipient mortality status will be ascertained at all follow-up time-points. Date and cause of death will be ascertained.

Supplementary Outcomes

Global Deterioration Scale (GDS) [63] τ . The GDS is a semi-structured rating of functional status in degenerative dementia. It has been successfully used in prior studies of dementia caregiver intervention with adequate reliability [5]. Ratings will be assigned for care recipient status based on interview with the caregiver. Ratings will be assigned by Drs. [name], [name], and [name] while remaining blinded to the participant's ESR/UC assignment. Care recipients with all-cause dementia will have scores ranging from 4 to 7 on this 0-7 point scale.

Revised Scale for Caregiving Self-Efficacy (SCSE) [64] τ . The SCSE is a 15-item scale consisting of three subscales (self-efficacy for: obtaining respite; responding to disruptive patient behaviors; and controlling upsetting thoughts about caregiving). Items are rated from 0-100 to indicate how confident a caregiver is in their ability to do certain activities (e.g., "How confident are you that you can control thinking about unpleasant aspects of taking care of [insert care recipient]?").

Medical Outcomes Study Short Form Health Survey (SF-12) [65] τ . The SF-12 is a brief self-report measure of overall health-related quality of life. Items relate to physical limitations and the extent to which pain and emotional problems interfere with activities over the past 4 weeks. Scores are calculated for Physical and Mental Health Composites and range from 0 to 100. Higher scores indicate better health-related quality of life.

Telephone Cognitive Screen (T-CogS) τ . The T-CogS was originally referred to as the Telephone Mini-Mental State Examination (TMMSE) [42]. The T-CogS is a 26-item, brief mental status examination that was designed to be administered over the telephone, based on the Mini-Mental Status Examination (MMSE) [43]. Scores range from 0-26. Scores on the T-CogS are strongly correlated with MMSE scores ($r = 0.88$, $p < 0.001$) [44]. An exclusion cutoff score of < 20 on the T-CogS was chosen to match a MMSE cutoff of < 23 . A telephone cognitive screen was specifically chosen to reduce travel burden for caregivers.

[[Assessment Timeline

An outline assessments and time-points at which they will be ascertained are show below:

Assessment	Screening	Baseline	3 month Booster	Intervention Period	6 month Follow-up	9 month Booster	12 month Follow-up	24 month Follow-up
Inclusion/Exclusion	X							
T-CogS*	X	X			X		X	X
Demographics	X	X			X		X	X
Primary Outcome								
ZBI*		X			X		X	X

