While these two studies are prime examples of successful caregiver interventions, it is unknown if REACH intervention effects last more than six months. ***Future studies with follow-up periods beyond six months post-intervention will enable more complete assessment of care recipient outcomes including LTC placement and mortality***; events which typically occur more distally [5].

Multicomponent dementia caregiver interventions without high cost burdens

While REACH-II served as large step forward in improving family-centered dementia care, these effects came at high resource costs including 13.5 hours of in-home visits, 1.5 hours of telephone sessions, and five additional telephone support group sessions. The REACH-VA clinical translation project, while moderately effective, will also be costly to implement on a large scale. Official patient care costs for this translational study have not yet been reported. Simply using time as a measure of resource intensity, REACH-VA required: nine hours of individual home visits and 1.5 hours of individual telephone session for a total of 10.5 hours of individual care time per caregiver, on top of five hours of telephone support group sessions and staff travel time for home visits.

Alternatives to resource intensive interventions aiming to enhance Veteran- and family-centered dementia care are needed. Low-cost, pragmatic interventions can fill a void in VA dementia care by providing caregiver rehabilitation to a large number of family members without causing high staff,

resource, and cost burdens. Using recent and growing advances in VA technology such as video telehealth to provide care to more Veterans and families will increase access to care and decrease cost burden to the VA.

2.A.1.F. Advancement of Clinical Practice

We propose to improve Veteran, family, and VHA outcomes through the study of a group-based education and skill-building rehabilitation (ESBR) intervention, targeted specifically to address limitations of prior studies including narrow diagnostic inclusions, proximal follow-ups, and the use of costly, resource-intensive interventions.

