A version of ESBR was piloted beginning October 2012 as a "Dementia and Alzheimer's Disease Education Series." The series was offered on the four Fridays of the month of October from noon – 1:00pm in the MIRECC (see Appendix 2 for content samples). Participation was open to Veterans with mild cognitive impairment, Veterans with early stage dementia, adult family members of all Veterans, and was also open to Veterans without dementia. The pilot was designed to have open attendance, in that attendees were invited to come to as many or as few sessions as they were able (knowing the series would recur monthly for the next few months). We did not gather follow-up data on potential study outcomes as the aim of this intervention pilot was to test feasibility and acceptance of the intervention.

During this initial pilot month, 12 participants attended some or all of the sessions. Individual session attendance ranged from one to seven participants. Participants consisted of 11 family caregivers of Veterans with dementia and one Veteran with dementia who attended with his spouse. Attendees were asked to provide anonymous feedback through an evaluation form at the end of each session. Feedback was requested (1 = Strongly agree; 2 = Agree; 3 = Neutral; 4 = Disagree; 5 = Strongly Disagree) on the following topics:

- The seminar was well organized.
- The seminar format was effective.
- The seminar content was informative.
- I learned something useful today about [major topic of the session].
- The seminar met my expectations and learning needs.

Feedback for all four sessions was positive. Participants responded with "strongly agree" or "agree" to all questions. The evaluation forms also contained a section for comments. The following comments were written:

- "very useful and informative."
- "This is a big help, thank you!"
- "Excellent! Thank you so much!"
- "Big help!"
- "This is great. Thank you for all this information!"

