[[Continuing with open attendance, in that attendees were invited to come to as many or as few sessions as they were able (knowing the series would recur monthly for the next few months), we continued to pilot the intervention content on a monthly basis (scaled back during the holiday season: December 2012 – January 2013) through April 2013, with individual session attendance ranging from one to eight participants. Four caregivers who lived near CBOCs phoned [name] to indicate their interest in the Series, but indicated that traveling to the main facility to attend was too difficult for them; video telehealth will enhance access to care for these types of caregivers. Two social workers (both from different CBOCs) also phoned [name] to request the intervention be extended to serve caregivers at their location.

Feedback from participants continued to be positive. Participants responded with “strongly agree” or “agree” to all evaluation questions.

The following additional comments were written:

- **“detailed information was great on the resources, their types of services offered, and easy access to them.”**
- **“Very informative regarding interactions with doctors.”**
- **“Very informative. Hope that we will find the resources needed for our family”**
- **“Looking forward to the next session”**
- **“May not only help me, but family and volunteer friends.”**
- **“Better than Excellent”**
- **“Continue to let me know about similar classes, etc. *****@*****.com”]]**

2.A.2.d. Summary of Preliminary Work

Our research team has a long record of accomplishment in the areas of neurodegenerative disease, cognitive decline, dementia, and caregiver health. Based on our preliminary work and pilot of ESBR, we anticipate that study recruitment goals will be met given the need for dementia caregiver education and skill-building both at VA Palo Alto and in surrounding areas served by the VAPAHCS. Caregivers of Veterans with dementia were accepting and appreciative of ESBR. Using video telehealth to deliver ESBR will enable broader access to dementia care services in more rural areas.

2.A.3. Research Design and Methods.

2.A.3.a. Approach

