Inclusion criteria -- Participants must:

- be adults (age ≥18)
- report distress associated with being the primary caregiver for a family member with all-cause dementia [23]
 - **[[reporting at least 2 of the following 6 items at baseline assessment: felt overwhelmed, felt like they often needed to cry, were angry or frustrated, felt they were cut off from family or friends, reported moderate to high levels of general stress, or felt their health had declined]]**
- **[[provide at least one hour of care (supervision or direct assistance) per week over the past 3 months (other sources of caregiving for the Veteran with dementia can also be utilized; e.g., respite, home health aide, other family members, etc.)]]**
- be proficient in spoken and written English
- be capable of providing informed consent

Exclusion criteria -- Potential participants will be screened and excluded for:

- current or lifetime history of any psychiatric disorder with psychotic features
- prominent suicidal or homicidal ideation
- having met DSM-IV criteria for drug or alcohol abuse or dependence (except nicotine) within the past six months
- presence of alcohol intoxication (by breathalyzer) or alcohol withdrawal (by exam) during study recruitment or participation
- diagnosis of probable or possible dementia
- a Telephone Cognitive Screen score of < 20
- participation in another caregiver intervention within the past year
- lack of regular access to a telephone
- illness that would prevent 24 months of study participation
- planned transfer of care receiver to another caregiver or nursing home within 12 months

2.A.3.c.1. Recruitment

We aim to recruit 150 participants who meet inclusion/exclusion criteria for the proposed project (ESBR-i: n = 50; ESBR-v: n = 50; UC: n = 50). Participants will be recruited primarily from the VA Palo Alto Health Care System (VAPAHCS), including major divisions (i.e., Palo Alto, Menlo Park, and Livermore) and community-based outpatient clinics (CBOCs) in the surrounding area (i.e., Capitola, Fremont, Modesto, Monterey, San Jose, Sonoma, and Stockton). We anticipate primary referral sources to include: Sierra-Pacific Mental Illness Research Education and Clinical Center (directed by [name]); VAPAHCS Dementia Committee (chaired by [name], consultant); VA Memory Clinic (directed by [name]); Geriatric Research, Education, and Clinical Center ([name], consultant, serves as Clinical Nurse Specialist at this Center); Stanford/VA Aging

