We estimated power based on the proposed mixed effects analyses considering the repeatedly measured outcomes. Based on these analyses, we converted the growth model parameter estimated to group difference in primary outcome at 12 month. Considering potentially nonlinear development of our outcomes, we allowed for nonlinear trend over time (specifically, we used a piecewise growth model). In our power estimation for primary hypothesis 1, over the 4 assessments, we assumed the attrition rate of 10% (6 month), 15% (12 month), and 20% (24 month). We assumed the reliability of the Zarit Burden Interview to be 0.7 based on prior studies demonstrating a range of intra-class correlation coefficients that vary based on time intervals between tests [59-61]. Prior studies of caregiver interventions, like many psychosocial interventions, have reported small to medium effect sizes. One such study specifically aimed to improve outcomes of caregivers of Veterans with all-cause dementia of the Alzheimer's type [23] and demonstrated effect sizes (Cohen's *d*) on caregiver burden and depression ranging from 0.26-0.33. Based on this study, we expect an effect size of $d=0.3$ on our primary outcome of caregiver burden, as measured by the Zarit Burden Interview [72], and designed our study to be powered accordingly assuming that mixed effects modeling will be used as the analysis method. Our primary hypothesis (Hypothesis 1) is that those in the intervention group ($n=50$ ESBR-i and $n=50$ ESBR-v) will show steeper decline in burden compared to the usual care ($n=50$ control) group. Under this scenario, the estimated power to detect the difference between the intervention (ESBR-i + ESBR-v) and the control group in terms of care burden is 0.83 ($d=0.3$, $\alpha=0.05$, two-tailed) at the 12-month follow-up. For the secondary analysis, we will monitor both clinical (effect size) and statistical (p -value) significance, with more emphasis on clinical significance, which will inform future trials.

2.A.3.e.9. Implementation Plan

The table below presents a general outline of the activities planned during the award period to ensure timely completion of the research plan, publication/presentation of results, preparation of future studies aiming to enhance Veteran- and family-centered care (i.e., VA Merit Award), and development of a dissemination plan for a successful intervention.

CDA-2 TIMELINE										
	Year 1		Year 2		Year 3		Year 4		Year 5	
Project Component										

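### Eligibility does not check before randomization that a caregiver can attend ESBR at a VA site, which leaves room for dilution or for selective replacement after randomization

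*Combined protocol and SAP*

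**What the plan says.** **Entry criteria (2.A.3.b).** The one criterion about access is the exclusion for "lack of regular access to a telephone". There is also an exclusion for illness that would prevent 24 months of participation. Neither list mentions travel, group sessions or attendance.

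**Screening and consent (2.A.3.d, 2.A.3.e.1).** Screening is mainly by telephone. Staff explain the study and its requirements. Consent is marked as face-to-face, and randomization follows it.

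**Delivery (2.A.3.e.3).** In-clinic participants come to a VA division or a community-based outpatient clinic (CBOC). Video participants do not join from home: "Participants will attend the ESBR sessions at the medical center division or CBOC most convenient to them". Dates and times are to be arranged around participants' schedules.

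**Dropouts.** Section 2.A.3.d replaces eligible participants who drop out before receiving any intervention. Section 2.A.3.e.1 does not replace those who drop out later, and says their data will be used. Section 2.A.3.e.8a invokes the intention-to-treat principle.

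**Power (2.A.3.e.8b).** The stated power for pooled ESBR against usual care (UC) "is 0.83 ($d=0.3$, $\alpha=0.05$, two-tailed) at the 12-month follow-up". Attrition from assessments is allowed for; failure to attend sessions is not mentioned.

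**The concern.** The criteria screen for the ability to be followed up but not for the ability to receive the intervention. Because follow-up is mainly by telephone, the two can come apart: a caregiver may complete every assessment without ever reaching a session.

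Once such a caregiver is randomized to ESBR, the plan can take one of two routes, and each has a cost.

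- **The caregiver stays in follow-up.** He or she counts in the ESBR group while receiving none of the sessions, which pulls the primary contrast toward zero.
- **The caregiver drops out before any session.** He or she is replaced. The ESBR arms then fill with people who could attend. UC participants receive printed materials and face no such hurdle, so the groups being compared are no longer those that randomization formed. The plan says that the data of later dropouts will be used but is silent on the data of those replaced. If they leave the analysis, this conflicts with the intention-to-treat statement.

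A check before allocation, applied alike to all three arms, reduces both problems without disturbing the randomized comparison.

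**Working it through.** **1. Inputs.** From 2.A.3.e.8b: 100 ESBR and 50 UC; d = 0.3; two-sided alpha 0.05; reliability of the burden score 0.7; attrition 10%, 15% and 20% at 6, 12 and 24 months; a piecewise growth model whose knot is not stated. The share f of analyzed ESBR caregivers who gain nothing is **not in the documents** and is an assumption throughout.

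**2. Reproducing the stated 0.83.** Power = Φ(d/SE − 1.96).

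- *Closed form.* With 15% attrition, 85 ESBR and 42.5 UC remain. With residual variance 1 − 0.7 = 0.3, SE = √0.3 × √(1/42.5 + 1/85) = 0.1029. Power = Φ(0.3/0.1029 − 1.96) = 0.830.
- *Piecewise mixed model.* With a knot at 6 months, a random intercept with intraclass correlation 0.7, equal baseline means and the planned attrition, SE = 0.1039. Power = Φ(0.3/0.1039 − 1.96) = 0.823.

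Both agree with the plan to within 0.01. Other plausible two-sided variants do not. With 15% attrition, a raw two-sample comparison gives 0.36, a change score 0.54 and ANCOVA 0.61. With the full attrition pattern, a knot at 12 months gives 0.62, and a knot at 6 months with free baseline means gives 0.73. The reproduction therefore rests on favourable but plausible choices.

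**3. Dilution, as an illustration.** If a share f of analyzed ESBR caregivers has zero effect, the pooled effect is 0.3 × (1 − f).

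| f (assumed) | Effective d | Power, SE 0.1029 | Power, SE 0.1039 |
|---|---|---|---|
| 0% | 0.300 | 0.830 | 0.823 |
| 5% | 0.285 | 0.791 | 0.783 |
| 10% | 0.270 | 0.747 | 0.739 |
| 15% | 0.255 | 0.698 | 0.690 |
| 20% | 0.240 | 0.645 | 0.637 |

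Non-attendance of 20% in only one ESBR arm is f = 10% of the pooled group.

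**4. How thin the margin is.** Power of 0.80 needs d = (1.96 + 0.842) × SE.

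- With SE 0.1029 this is 0.2883, so f = 1 − 0.2883/0.3 = 3.9%.
- With SE 0.1039 it is 0.2911, so f = 3.0%.

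**5. Cost of buying the power back with numbers.** In the closed form, UC completers needed for power 0.83 = 1.5 × 0.3 × (1.96 + 0.954)² / d².

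- f = 10%: 53 completers; 53/0.85 rounds up to 63 enrolled per arm, or 189 in total.
- f = 20%: 67 completers; 67/0.85 rounds up to 79 per arm, or 237 in total.
- f = 0: the same rounding gives 153, against the 150 planned.

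**6. The other route.** Selective replacement cannot be put into a number from the documents. It does not lower the pooled d by the formula above; it changes who is compared with whom.

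**The case against.** Much of the case on the other side stands.

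- **The replacement rule narrows dilution.** Someone who cannot reach a session and drops out is replaced and does not dilute the contrast. Only non-attenders who remain in follow-up do. This stands, though it exchanges one problem for another.
- **The plan already lowers the barrier.** It offers the most convenient site and flexible dates (2.A.3.e.3), and reminders and 25 dollars per session or assessment (2.A.3.c.2). Recruitment draws largely on the network that hosts the sessions.
- **The pilot is weak evidence (2.A.2.c).** Four caregivers living near CBOCs reported that "traveling to the main facility to attend was too difficult for them". That concerns the main site, and the plan presents video delivery as the answer. "Individual session attendance ranged from one to seven participants" describes the first pilot month, a series with open attendance, so it does not measure inability to attend scheduled trial sessions.
- **The consent step cannot be judged.** Consent pages are not in the file. The explanation of requirements and the face-to-face consent may deter some who cannot travel, but neither is an eligibility criterion.
- **Zero effect is a simplification.** Session materials are to be provided to each participant in the intervention arms, so a non-attender may gain something.
- **The planned effect may already contain some non-adherence.** "we expect an effect size of $d=0.3$ on our primary outcome of caregiver burden" rests on a study that "demonstrated effect sizes (Cohen's *d*) on caregiver burden and depression ranging from 0.26-0.33", and these are observed effects. However, section 2.A.1.E describes that program as using "nine hours of individual home visits and 1.5 hours of individual telephone session", plus telephone support groups, so non-attendance caused by caregiver travel is unlikely to be built in.
- **Representation.** The plan calls the intervention pragmatic and seeks wider rural access. Excluding people who cannot travel narrows the population, and either choice can be defended.

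A reader might infer that the trial will fall below its stated power, or that only a pre-randomization question can keep non-attenders out of the contrast. The documents support neither: they give no non-attendance rate, and the replacement rule removes some of these caregivers.

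**Conclusion.** The gap is real: both ESBR modes need a visit to a VA site, and no eligibility criterion checks before randomization that the caregiver can make it. The consequence depends on how the replacement rule is applied. It is dilution from non-attenders who stay in follow-up, selection of attenders in the ESBR arms alone, or some of each.

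The power figures are conditional. They assume that the chosen model variants resemble the plan's own calculation, that f takes the values shown, and that non-attenders gain nothing. They show sensitivity, since some 3% to 4% is enough to pass below 0.80, and they do not predict a loss. Nor could a screening question recover all of it: later illness, a crisis in care or loss of interest would still keep some people away. This is a cheap improvement worth making, and not a demonstrated power failure.

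**What to change.** Add an inclusion criterion in 2.A.3.b, checked in every caregiver before randomization: able and willing to attend the four group sessions and the two boosters at a VAPAHCS division or CBOC under either delivery mode.

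In 2.A.3.d and 2.A.3.e.8a, state that every randomized caregiver stays in the primary analysis, whether or not a session was attended and whether or not a replacement was enrolled.

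The cost is one eligibility line, one screening question and one sentence on the analysis population. Caregivers who cannot reach any VA site will not be represented, which should be stated as a limit on generalizability, and screening failures will rise slightly.
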